Some of the most widely used pharmacological methods are topical anaesthetics like EMLA. In addition, we have useful drugs in the treatment of anxiety associated with procedures, such as nitrous oxide or intranasal midazolam. (5). Non-pharmacological methods can complement pharmacological methods. They are generally effective and economical. They can be classified into (6):

- Support methods: promote psychosocial assistance to the child. Example: parental presence during procedures.
- Cognitive methods: try to influence the thoughts and imagination of children. Example: active or immersive distraction (playing, holding a conversation) and passive or non-immersive distraction (music therapy, watching TV).
- Behavioural methods: they are based on the child's own actions. Example: deep breathing.
- Physical methods: involve the sense of touch. Example: caresses, hugs.

Virtual reality as a method of non-pharmacological analgesia

Play, in a broad sense, is the main occupation of healthy children, so that through play their development is promoted and constitutes a means of communication and expression(7). To date, studies have been conducted on various types of gambling. In a literature review in which the literature published between 2005 and 2015(8) was reviewed, it is stated that different games or toys have been shown to be effective in reducing pain and anxiety generated during venepuncture. Among them we find music tables, portable video games, virtual reality glasses and the kaleidoscope.

Virtual reality, like the other types of game, is another method of active distraction. However, it has its own characteristics that differentiate it from play therapy in general. Virtual reality is defined as "a computer-generated, interactive, three-dimensional environment into which the person is introduced"(9). There are numerous studies conducted in paediatric age with virtual reality to reduce pain associated with procedures. Most of them have been performed in hospitalized patients or patients of the Emergency Department, who need intravenous insertion or blood test. In a randomized clinical trial conducted in our country with children aged 6 to 14 years(10), pain and anxiety associated with venepuncture and intravenous insertion were evaluated in a group that used virtual reality and in a control group with usual care (distraction with objects, questions of daily life).

In this study, they obtained lower means of pain and anxiety in the virtual reality group, although without statistically significant differences, probably due to the small sample size (17 participants).

Management of pain associated with procedures in Xàtiva-Ontinyent Health Department

In Xàtiva-Ontinyent Health Department, a population of 194,799 inhabitants is served. Of these, 26,165 are under the age of 15. Scheduled blood tests are performed at health centers of the department and at the two hospitals.

Non-pharmacological analgesia methods such as the presence of parents, distraction of the patient talking about daily life and pharmacological analgesia methods such as the application of EMLA are usually used.

1- JUSTIFICATION

In Spain there is a high prevalence at the national level of paediatric pain, often related to procedures such as venepuncture. Currently, due to the rise of new technologies, there are numerous studies carried out with virtual reality as a method of analgesia, but they are very diverse in terms of the type of patient and procedure.

With this project, we intend to verify the effectiveness of virtual reality in reducing pain and anxiety associated with scheduled blood collection in the paediatric population.

2- HYPOTHESIS

The use of virtual reality glasses decreases the pain associated with venepuncture in children.

3- OBJECTIVES

Main objective: to determine the effectiveness of the use of virtual reality in reducing pain and anxiety associated with scheduled blood tests.

Secondary objectives:

- To evaluate the satisfaction of parents or caregivers.
- To evaluate the satisfaction of the professional in charge of venepuncture.

4- PATIENTS AND METHODS

5.1- STUDY DESIGN

Multicenter randomized clinical trial carried out in 5 Health Centers and in the 2 Hospitals of the Xàtiva-Ontinyent Health Department, in which scheduled blood extractions are performed. The test will be carried out following the CONSORT guidelines(11). Patients are distributed in a 1:1

ratio to the intervention group (use of virtual reality during blood test) and to the control group (usual care). In the intervention group, OCULOS QUEST 2 Virtual Reality glasses will be used in which a video will be displayed from the beginning of the technique (preparation of material) to the end (compression). In the control group, venepuncture will be performed through usual care (distraction by nursing talking to the patient or through the use of topical anaesthetic in chronic patients undergoing multiple extractions).

5.2- SELECTION OF THE SAMPLE

The patients potentially eligible for the study will be those who come to perform a routine blood test to the centers participating in the study to perform a blood collection during the study recruitment period.

The Questionpro calculator (<https://www.questionpro.com/es/calculadora-de-muestra.html>) was used to calculate the sample size. With a confidence level of 95%, a margin of error of +/- 5, and an available population of 70 children, the required sample is 60 patients.

- Inclusion criteria:

Children aged between 7 and 12 years, who agree, both they and their parents or tutors, to participate in the study by signing the informed consent.

- Exclusion criteria:

- Children under 7 years old for not having completed the development of visual function(12).
- Children over 12 years old, since by expanding the age range, it would be a very heterogeneous sample.
- Not having signed the informed consent.
- Children with psychomotor and neurocognitive delay, due to the difficult assessment of anxiety.
- Children with visual or hearing disabilities, because they cannot adapt virtual reality glasses to their conditions.

- Randomization:

The sequence that will be carried out to carry out the study is:

- 1- Inform and recruit the participant.
- 2- Sign informed consent.
- 3- Open the envelope with the randomization.
- 4- Perform the technique (blood test with usual care or with virtual reality).

[figure not shown]
- Pseudonymisation:

After including patients in the study, they will be assigned a code that will be formed by the initials of the two surnames followed by the last 3 digits of the number of the health card number.

5.3- OUTCOME MEASURES

- Primary outcome measures:

- Pain associated with venepuncture (Visual Analogue Scale) (Figure 1) (13)

- Anxiety associated with venepuncture: Groningen distress scale (Table 1) (14)

Table 1. Groningen distress scale			
GRADE	STATUS OF CHILD	MUSCLE TENSION	CRY
1	Calm and no cry	No	No
2	Tension without crying	Clenches fists, pale knuckles, grinds teeth, closes eyes, muscle contraction, body stiffness	No
3	Tension with some cry	Like 2	Intermittent
4	Tension and continuous cry	Like 2	Continuous
5	Aggression / screams / physical resistance	Agitation, violent movements of the body and extremities, a lot of resistance to the procedure	Continuous, screams

- Secondary outcome measures:

- Number of attempts for analytics (1 to 5).
- Time required for analysis (minutes).
- Difficulty level of the technique (easy, normal or difficult)
- Parents satisfaction (1 = unsatisfied, 10 = very satisfied)
- Nurse anxiety (1 = totally calm 10 = very anxious)
- Patient age at the moment of venipuncture (years)
- Patient sex
- Venipuncture in the last 6 months (yes or not)

- Parental presence at the moment of venipuncture (yes or not)

5.4- ETHICAL ASPECTS

Prior to participation in the study, the parents or guardians of the patients will sign the informed consent.

5.5- STATISTICAL ANALYSIS

All the information obtained in the study will be tabulated in a database designed for this purpose in the SPSS program (Statistical Package for the Social Sciences) version 22, maintaining the anonymity of the patients. Descriptive analysis of the variables will be performed. The qualitative variables will be expressed with frequency distribution. Chi square will be applied to compare the qualitative variables and Mann Whitney U for ordinals. A significance level of $p < 0.05$ is established.

5- BIBLIOGRAPHY

1. International Association for the Study of Pain (IASP) [Internet]. IASP press. 1994. Disponible en: <https://www.iasp-pain.org/Education/Content.aspx?ItemNumber=1698>
2. Mínguez Navarro MC. Utilización de un sistema de videodistracción para disminuir la ansiedad y el dolor en niños durante la venopunción en un servicio de Urgencias Pediátricas [tesis doctoral]. Madrid: Universidad Autónoma de Madrid, Facultad de Medicina; 2013.
3. Reinoso Barbero F. Prevalencia del dolor en los pacientes pediátricos hospitalizados en España. Rev Esp Anestesiol Reanim [Internet]. 2013;60(8):421–3. Disponible en: <http://dx.doi.org/10.1016/j.redar.2012.12.013>

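### The secondary objective on the professional's satisfaction has no matching outcome; the plan records nurse anxiety instead

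*Combined protocol and SAP*

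**What the plan says.** Section 3 (Objectives) lists two secondary objectives: "To evaluate the satisfaction of parents or caregivers" and "To evaluate the satisfaction of the professional in charge of venepuncture".

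Section 5.3 (Outcome measures) gives parents an item that matches the first objective: "Parents satisfaction (1 = unsatisfied, 10 = very satisfied". For the professional it gives "Nurse anxiety (1 = totally calm 10 = very anxious". It also asks for "Difficulty level of the technique (easy, normal or difficult", which describes the procedure.

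Section 5.5 (Statistical analysis) assigns tests by type of variable: "Chi square will be applied to compare the qualitative variables and Mann Whitney U for ordinals". It defines no derived variable and does not link any outcome to an objective.

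**The concern.** An objective can be answered only if something is recorded that measures it. Here the protocol names satisfaction as the construct for two groups, parents and professionals, but supplies a satisfaction item only for parents. The professional is asked about anxiety.

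As the plan stands, the report can go one of two ways. The objective may be left without a result. Or nurse anxiety may be presented as if it answered the satisfaction question. The second course would attach the wrong name to the measurement. It would also invite an error of direction, since a high score is favourable on the parent item and unfavourable on the nurse item.

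The rating belongs to the moment of the procedure, so an item missing from the data sheet cannot be reliably recovered afterwards.

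**Working it through.** No figure in the plan is at stake, so the check sets each secondary objective against every listed outcome.

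**Step 1. Objectives.** Section 3 gives two: parent or caregiver satisfaction (A) and professional satisfaction (B).

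**Step 2. Outcomes.** Section 5.3 gives two primary outcomes, both about the child: pain on a visual analogue scale and anxiety on the Groningen scale. Neither bears on A or B. It then gives nine secondary items:

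| Secondary item (5.3) | What it describes | Measures A? | Measures B? |
|---|---|---|---|
| Attempts | procedure | no | no |
| Time taken | procedure | no | no |
| Difficulty, three levels | procedure | no | no |
| Parent satisfaction, 1 to 10, 10 best | parent | **yes** | no |
| Nurse anxiety, 1 to 10, 10 worst | professional | no | no |
| Age | child | no | no |
| Sex | child | no | no |
| Recent venepuncture | child | no | no |
| Parent present | setting | no | no |

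**Step 3. Count.** Objective A is matched by 1 of 9 items and objective B by 0 of 9. So 1 of 2 secondary objectives has an outcome.

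**Step 4. Could another item stand in for B?**

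- *Nurse anxiety.* The anchors run from calm to anxious, so anxiety is what is recorded. A nurse can be calm and dissatisfied, or tense during the procedure and satisfied with the result. Reversing the score (11 minus the rating) would align its direction with the parent item, but the result would be calmness, not satisfaction.
- *Difficulty, attempts, time.* These may influence satisfaction, but they describe how the procedure went.
- *A rule in section 5.5.* There is none. The section selects tests by variable type and sets the significance level, and it makes no item a proxy for another.

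**Step 5. Could the item have been lost from the text?** This is unlikely. Section 5.3 lists its outcomes as text, and the only figure it cites belongs to the pain scale.

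**The case against.** The case on the other side accepts that the mismatch exists and disputes how much it matters.

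- *Scale direction is not an error.* This is correct. High meaning worse is natural for an anxiety item, and both sets of anchors are printed. The opposite directions matter only if the nurse item is read as satisfaction. The defect is the construct.
- *The plan never says it will report anxiety as satisfaction.* This is also correct. The mislabelling is a foreseeable consequence, not a stated intention. The documented fault is an objective with no outcome, and that is enough.
- *The plan does collect data on the professional's experience.* Anxiety, difficulty, attempts and time all bear on it. None measures satisfaction, so the accurate statement is that there is no direct measure.
- *It may be a slip of wording or translation.* It may, but the documents do not settle this, and either the objective or the outcome list would still need correcting.
- *Analysing a new item like parent satisfaction may be too simple.* With 60 patients over 7 sites, about 60 / 7 = 8.6 per site, one nurse may rate several children, and a plain Mann-Whitney test would treat those ratings as independent. The number of nurses is not stated, so this is a possibility only. It applies equally to the nurse anxiety item already planned. It is a reason for care in the analysis, not a reason to leave the objective unmeasured.
- *The effect is limited.* The hypothesis, main objective, primary outcomes, randomisation and sample size are untouched. This stands, and it sets the weight of the point.

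**Conclusion.** The concern holds. One of the two secondary objectives has no outcome that measures it, and nothing in sections 5.3 or 5.5 fills the gap. The conclusion rests on the documents' own lists and needs no numerical assumption. It does assume that satisfaction and anxiety are different constructs, which the protocol supports by giving them different anchors.

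The point should be corrected, but it does not threaten the trial's main conclusion. Its reach is confined to what can be claimed about the professionals who perform the venepuncture.

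**What to change.** **Preferred, if the data sheet can still be changed.** Add to section 5.3 a rating of satisfaction by the professional who performs the venepuncture, on the same 1 to 10 anchors as the parent item. It should be completed straight after the blood test in both arms. Word it so that it applies equally with and without the headset, because the control arm does not use one. Compare the arms with the Mann-Whitney U test already planned for ordinal variables. Keep nurse anxiety as a separate outcome under its own name. It would be prudent to record a code for the nurse, so that repeated ratings by one person can be seen and allowed for.

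**If recruitment is too far advanced.** Reword the second secondary objective in section 3 so that it concerns the professional's anxiety. Date the change, make it before the data are analysed, and disclose it in the report. The trial should then draw no conclusion about professional satisfaction.

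**Cost.** The first route costs one extra item on the data sheet, plus a nurse code if that is added. The second costs a one-line change to the objective. Neither affects the sample size or the primary analysis.

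### The sample of 60 is a survey size for one proportion in a pool of 70 children; it does not justify the two-arm comparison, and +/-5 is not that comparison's precision

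*Combined protocol and SAP*

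**What the plan says.** Section 5.2 (Selection of the sample) names an online calculator that "was used to calculate the sample size". It gives three inputs and the answer: a 95% confidence level, "a margin of error of +/- 5, and an available population of 70 children, the required sample is 60 patients". That is the whole rationale.

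The rest of the plan describes a comparative trial:

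- The main objective in section 3 is "to determine the effectiveness of the use of virtual reality in reducing pain and anxiety associated with scheduled blood tests".
- Section 5.1 says "Patients are distributed in a 1:1" "ratio to the intervention group (use of virtual reality during blood test) and to the control group (usual care"), which is 30 per arm if 60 are recruited.
- Section 5.3 lists two primary outcomes: "Pain associated with venepuncture (Visual Analogue Scale) (Figure 1) (13") and "Anxiety associated with venepuncture: Groningen distress scale (Table 1) (14"), the latter graded 1 to 5.
- Section 5.5 says "Chi square will be applied to compare the qualitative variables and Mann Whitney U for ordinals", with significance at p < 0.05.

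No section gives a target difference, a standard deviation, an expected grade distribution, a power or a dropout allowance.

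**The concern.** Confidence level, margin of error and population size are the inputs for estimating one percentage in a closed group. A randomised comparison is sized from the difference to be detected, the variability of the outcome, the error rate and the power. If 60 came from the first kind of calculation, it carries no information about the second.

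What is at stake is how the result can be read. The introduction describes an earlier randomised trial of virtual reality with 17 participants and attributes its lack of significance to small size. The sponsor therefore accepts that size governs what a null result means. Yet the plan never says what difference in pain or distress 30 per arm can detect, or whether a difference of that size is one it considers important. A non-significant result here would be just as hard to interpret.

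**Working it through.** **1. Reproducing the plan's 60.** Inputs from section 5.2: z = 1.96 for 95% confidence, margin e = 0.05 and pool N = 70. Two things are inferred because the plan does not state them: +/-5 means percentage points, and p = 0.5.

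- n0 = z² p(1−p)/e² = 1.96² × 0.25/0.05² = 384.16
- n = n0/(1 + (n0 − 1)/N) = 384.16/(1 + 383.16/70) = 59.34, rounded up to 60

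With p = 0.4 the formula gives 58.97 (59), and with p = 0.3 it gives 57.67 (58). Any p from about 0.41 to 0.59 also rounds up to 60, so the match identifies the method rather than an exact p.

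**2. What drives that answer.** With the same confidence and margin and only the pool changed:

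| Pool | Formula | Rounded up |
|---|---|---|
| 65 | 55.7 | 56 |
| 70 | 59.3 | 60 |
| 80 | 66.4 | 67 |
| 100 | 79.5 | 80 |
| 200 | 131.8 | 132 |

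The treatment effect does not enter at all.

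**3. What +/-5 describes.** For 60 of 70 children and one proportion near 0.5, the margin is 1.96 × √(0.25/60 × 10/69) = 4.8 points. For a difference in proportions between two arms of 30 it is 1.96 × √(2 × 0.25/30) = 25.3 points, about five times wider. For a difference in means it is 1.96 × √(2/30) = 0.51 SD.

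**4. What 30 per arm delivers for VAS.** Assumptions: all 60 analysed, two-sided alpha 0.05 (the plan does not state sidedness), Mann-Whitney test, normal shift. Simulated power (40,000 runs, type I error 0.050):

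| Standardised difference | Power |
|---|---|
| 0.5 | 0.457 |
| 0.6 | 0.603 |
| 0.75 | 0.796 |
| 0.8 | 0.843 |

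- If the SD were 2 to 3 points on a 0-10 scale (assumed), 0.75 SD is 0.75 × 2 = 1.5 to 0.75 × 3 = 2.25 points.
- With whole-number scores and 8%, 16% or 28% of controls at zero, power at an underlying 0.75 SD shift is 0.783, 0.776 or 0.747.
- The Hodges-Lehmann 95% interval has a mean half-width of 0.53 SD for continuous scores (coverage 0.953).
- For 80% power at 0.5 SD, n per arm = 2 × (1.96 + 0.842)²/0.5²/0.955 = 65.8, so 66 per arm or 132 in total.

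**5. Groningen grade.** Tie-corrected Mann-Whitney, proportional odds in favour of virtual reality, 30 per arm. All five control distributions are assumptions.

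| Assumed control grades 1-5 (%) | Odds ratio for about 80% power |
|---|---|
| 20/35/25/12/8 | 3.9 |
| 35/40/15/7/3 | 4.2 |
| 50/35/10/4/1 | 4.8 |
| 65/25/6/3/1 | 7 |
| 75/18/4/2/1 | 13 |

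There is no single detectable odds ratio: it rises steeply as more control children are already calm.

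**The case against.** The other side can fairly say that nothing here shows 60 to be wrong. Patients, allocation and outcomes stay as they are, so this is a gap in justification rather than a flaw that produces a false conclusion. The plan uses +/-5 only as a calculator input and never claims it as the precision of the treatment comparison. Keeping 60 also looks premature if the sponsor may answer that 0.5 SD matters: section 5.2 does not say that the pool of 70 is fixed, and the department has 26,165 residents under 15. Finally, there are two primary outcomes, and the 80% figure gives VAS the full 0.05.

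Parts of this stand. The plan does not attach +/-5 to the comparison in words, but it is the only precision figure offered, so a reader may take it that way. The alpha point is correct as a sensitivity: if 0.05 were split into 0.025 per outcome, power at 0.75 SD would be about 70%, and 80% would need about 0.84 SD. Section 5.5 states an unsplit p < 0.05, however, so the 80% figure matches the plan as written. The +/-0.53 SD assumes continuous scores; with whole-number scores the interval is conservative (coverage about 99%). Other interval methods would also serve. Keeping 60 is the inexpensive route and fits the stated pool; whether to widen recruitment is the sponsor's decision once it has named the difference that matters.

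None of this supplies the missing link between 60 and a between-arm difference.

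**Conclusion.** The concern holds. The arithmetic behind 60 is right for a survey; the method is wrong for this trial. The figure follows from the size of the pool and would be the same whatever virtual reality does to pain or distress. Sixty is therefore not shown to be required.

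Sixty could be adequate if the effect is about 0.75 SD or larger on VAS. For 0.5 SD it gives slightly less than an even chance of a significant result. These figures rest on 30 analysed per arm, two-sided 0.05 for each outcome and a normal shift. The SDs and Groningen distributions are assumptions, since the documents give none. The survey diagnosis depends on none of these; it rests on the exact reproduction of 60.

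**What to change.** 1. In section 5.2, remove the +/-5 margin and the statement that 60 is required. Give the actual reason for 60, for example the number of children available. The sponsor must confirm that reason first, so that 60 is not left without a rationale.
2. Add what the size delivers: *At two-sided alpha 0.05 with all 60 analysed (30 per arm), the Mann-Whitney test has about 80% power for a standardised VAS difference of 0.75 and about 46% for 0.5, assuming a normal shift.* If alpha is later divided between the two primary outcomes, these figures must be recalculated.
3. Have the sponsor state whether 0.75 SD is the difference it considers important. If a smaller one matters, give the power at that difference and describe the trial as limited for it. For scale, 0.5 SD at 80% power needs about 132 children, against the 70 stated as available.
4. For Groningen, either omit power or show it beside each assumed control distribution. Do not quote one odds-ratio range.
5. In section 5.5, name Mann-Whitney for VAS, since the power statement relies on it and the text refers only to ordinal variables. Report a 95% confidence interval for each primary outcome. Suitable choices are the Hodges-Lehmann difference for VAS and, for Groningen, the probability that a child in the virtual reality arm has a lower grade than a control child, ties counted as half.

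Cost: no extra patients and no change to allocation. It takes new wording in 5.2, two intervals in 5.5 and two answers from the sponsor. The price is a little more analysis work and a less flattering statement of precision.
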